Study Design	 within 3 months within 12 months Incidence of a MaxTack[™] Motorized Fixation device deficiency (DD) (e.g., insufficient tack penetration, loose tacks, tack(s) migration, tacker battery issue, etc.) on the day of the index procedure. Operative time for mesh fixation, defined as the time elapsed from the initiation of the mesh fixation process with MaxTack[™] to its completion. Surgeon satisfaction as assessed by Surgeon Satisfaction Questionnaire postoperatively. Length of hospital stay after minimally invasive ventral hernia repair procedure where the MaxTack[™] Motorized Fixation Device was used for fixation. Change in subject-reported pain at the hernia site evaluated with Numeric Rating Scale (NRS) score from 0 to 10 at screening and compared to the following timepoints: at Month 1 at Month 12 Change in subject Quality of life (QoL), as measured through the administration of the Hernia Quality of Life (HerQLes) questionnaire, evaluated at screening and compared to the following timepoints: at Month 1
	performance and safety of the MaxTack [™] Motorized Fixation Device used for fixation in minimally invasive ventral hernia repair procedures. The study will be conducted at approximately 10 sites within the United States. However, additional sites in other regions may be added as needed to meet study objectives.
	Upon obtaining IRB/EC approvals, subjects who have signed an informed consent form and who meet eligibility criteria will be enrolled in the study. Subjects will undergo elective minimally invasive ventral hernia repair

AFFIX (MaxTack [™] Motorized Fixation Device) Clinical Investigation Plan				
MDT23014	Revision	3.0	Page 15 of 97	Medtronic
	surgery using mesh for reinforcement. The procedure will utilize the MaxTack [™] Motorized Fixation Device for mesh fixation and evaluations will be conducted at various time points, including Screening, Operative, Discharge, and postoperative visits at Month 1, Month 3, and Month 12.			
	The study duration is estimated to be approximately 13 months of recruitment followed by a 12-month postoperative follow-up period (+ 45 Days). The primary analysis will be conducted when all subjects have completed their Month 3 follow-up visits (or exited the study) and may be used for regulatory and publication purposes. The final analysis, intended for comprehensive assessment, will be conducted when all subjects have completed their Month 12 follow-up visit and / or exited the study.			

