5.1.2 Secondary Objectives

The secondary objectives of this study are to evaluate the safety and performance of the MaxTack[™] Motorized Fixation Device when used for fixation in minimally invasive ventral hernia repair procedures within 12 months postoperatively.

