5.2.2 Secondary Endpoints

The secondary endpoints will include:

- Incidence of Surgical Site Occurrence (SSO) which are the following Adverse Events (AEs) related to the study device, mesh, and / or study procedure and defined as Seroma, Hematoma, Surgical Site Infection (SSI), bleeding at tack implantation site following the MaxTack[™] Motorized Fixation Device used for fixation in minimally invasive ventral hernia repair procedures at the following timepoints:
 - by Discharge
 - o within 1 month
 - within 3 months
 - within 12 months
- Incidence of SSO requiring Procedural Intervention (SSOPI), which are the following AEs related to the study device, mesh, and/or study procedure and defined as Seroma, Hematoma, Surgical Site Infection, bleeding at tack implantation site following the MaxTack[™] Motorized Fixation Device used for fixation in minimally invasive ventral hernia repair procedures at the following timepoints:
 - by Discharge
 - o within 1 month
 - o within 3 months
 - o within 12 months
- Incidence of hernia recurrence following the MaxTack[™] Motorized Fixation Device used for fixation in minimally invasive ventral hernia repair procedures. The evaluation of hernia recurrence will be performed via a Valsalva maneuver during a physical examination and confirmed per site standard of care medical imaging, if necessary, at the following timepoints:
 - \circ within 1 month
 - o within 12 months
- Incidence of hernia recurrences resulting in reoperation, defined as an operative procedure performed with the specific goal of repairing the recurrent hernia, at the following timepoints:

- o within 1 month
- \circ within 3 months
- within 12 months
- Incidence of MaxTack[™] Motorized Fixation Device deficiencies (e.g., insufficient tack penetration, loose tacks, tack(s) migration, tacker issue battery etc.) on day of the index procedure.
- Operative time for mesh fixation, defined as the time elapsed from the initiation of the mesh fixation process with MaxTack[™] to its completion
 - Surgeon satisfaction as assessed by Surgeon Satisfaction Questionnaire postoperatively.
 - Length of hospital stay after minimally invasive ventral hernia repair procedure where the MaxTack[™] Motorized Fixation Device was used for fixation.
- Change in subject-reported pain at the hernia site evaluated with Numeric Rating Scale (NRS) score from 0 to 10 at screening and compared to the following timepoints:
 - o at Month 1
 - o at Month 3
 - o at Month 12

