The MaxTack[™] Motorized Fixation Device is indicated for use in the fixation of hernia mesh to soft tissue during minimally invasive ventral hernia repair procedures. The subject population will include adult subjects 18 years or older who are undergoing ventral hernia repair by minimally invasive surgeries. Excluding subjects with high risk factors such as infection, American Society of Anesthesiologists (ASA) score of 4, 5, or 6, history of three or more hernia repair surgeries, history of allergic reaction to device components, or a Body Mass Index (BMI) more than 45, may mitigate procedure or device performance risks to the subjects. Restricting enrollment to subjects who have a life expectancy of 3 years or more may aid in ensuring the subjects can complete 12 months of follow-up.

Rationale for Chosen Endpoints and Timing of Endpoints

This post-market study will assess the performance and the safety of the MaxTack[™] Motorized Fixation Device during minimally invasive ventral hernia repair procedures. Subjects will be evaluated at the screening, operative, discharge, Month 1, Month 3, and Month 12 visits.

The primary endpoint of the performance of MaxTack[™] by measuring the incidence of hernia recurrence within 3 months postoperatively has been selected for this study. The absorbable tacks need to retain strength long enough to hold the mesh in place until sufficient ingrowth occurs. Wound healing and mesh integration processes occur up to 12 weeks. If the tacks fail in terms of strength or there is a deficiency, it should be observed within 3 months and may lead to a hernia recurrence during this period. For this reason, having a primary endpoint within the 3 months is appropriate.

The secondary endpoints further evaluate the performance and safety of MaxTack[™]. These include evaluations at Month 1, 3, and 12. Subject follow-up is until 12 months postoperative since the MaxTack[™] tacks will be fully absorbed by 12 months. Based on similar clinical studies, the endpoints were chosen to

AFFIX (MaxTa Clinical Invest				
MDT23014	Revision	3.0	Page 26 of 97	Medtronic

best characterize the performance and safety of MaxTack[™], as well as to evaluate the compatibility and ease of use of MaxTack[™].

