According to ISO 10993-1, the MaxTack[™] Motorized Fixation Device is an implantable device (absorbable tacks) in long-term contact (> 30 days) with tissues. The absorbable tacks do not contain any medicinal substances, animal tissues, or blood components.

MaxTack[™] involves an implantable component, which is absorbable. The tack is made up of a copolymer poly (glycolide-co-L-lactide) (PGLA). This copolymer degrades and is absorbed by hydrolysis to glycolic acid and lactic acid, which are then metabolized by the body. The absorption profile of PGLA in the first two weeks after initial implantation is minimal, with significant absorption from three to five months. Following this significant breakdown, the polymer absorption is essentially completed prior to one year.

In view of the detailed consideration of all the relevant data, the biological safety evaluation of MaxTack[™] has been found compliant with the biological safety requirements of ISO 10993-1, Ministry of Health, Labor and Welfare (MHLW) and FDA guidance on the use of International Standard ISO 10993-1, "Biological evaluation of medical devices - Part 1: Evaluation and testing within a risk management process".

All materials that may contact tissues and/or body fluids are presented in Table 1.

MaxTack [™] Motorized	Materials	Subject Contact	
Fixation Device Component			
Shaft	304L Stainless Steel with laser etched logo	Limited subject contact (less than 24 hours)	
Implant (Tack)	L1 Polymer: Absorbable Synthetic Polyester [poly (glycolide-co-L-lactide) (PGLA)]	Greater than 30 days	

Table 1: Materials in Contact with Tissues and/or Body Fluids

At the time of document approval, $MaxTack^{TM}$ is 510(k) cleared in the United States (US). There is no anticipated change in the product during the course of the study.

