11.1 Potential Risks

Medtronic follows rigorous Quality Assurance and Control procedures throughout the life of a product, from the business analysis phase through development, market release, and post-market surveillance. The risk analysis process for the AFFIX Study, MaxTack[™] Motorized Fixation Device is being performed in accordance with ISO 14971. Overall, the residual risk for the MaxTack[™] Motorized Fixation Device was deemed acceptable.

The potential risks of the MaxTack[™] Motorized Fixation Device have been described in the Instructions for Use (IFU) and are summarized below. As with any device, there is always a risk of a rare or previously unknown side effect developing from the treatment or use of the device. The IFU will be updated should a new risk become identified.

Risks associated with the use of any Tack Fixation devices may include improper tack placement, deployed tacks having insufficient holding force (resulting in tack/mesh migration, adhesions, erosion, recurrence and damaged mesh), excessive tack penetration, tack penetration through great vessels or cardiac

AFFIX (MaxTack [™] Motorized Fixation Device) Clinical Investigation Plan				
MDT23014	Revision	3.0	Page 48 of 97	Medtronic

structures, tack impinging on nerves, and foreign body reaction (resulting in "meshoma" formation, tack hernias, chronic pain, and infection). Risks associated with the MaxTack[™] Motorized Fixation Device include but are not limited to: seroma, fistula, perforation, hernia recurrence, bowel entrapment, strangulated bowel, tissue damage/trauma, cardiac tamponade and/or damage to pericardium, bleeding/hematoma, acute/chronic pain, nerve damage, infection, allergic reactions to the components of the product, burns, environmental contamination, inflammatory reaction, visceral adhesions, vascular injury, visceral injuries, and injuries to operator. Investigators participating in this study are experienced with the known risks related to standard of care for ventral hernia repair procedures. Due to the nature of the procedure and use of multiple products (tacks and mesh), it may be hard to differentiate between risk associated with the tack vs. those associated with the mesh, and / or the procedure. There are no known risks associated with an interaction of the tacks with any concomitant medication.

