11.4 Risk-Benefit Rationale

As described in the IFU for the MaxTack[™] Motorized Fixation Device, a ventral hernia repair procedure involving a tacker involves risk. These complications are associated with both the procedure itself as well as the devices being used. For patients who are candidates for the study, the benefits of using the MaxTack[™] Motorized Fixation Device during their hernia repair procedure may outweigh these risks.

In conclusion, the MaxTack[™] Motorized Fixation Device has been shown to have a favorable benefit-risk profile based on the criteria of the target population and the risks and benefits potentials of the device.

12. Adverse Events and Device Deficiencies

For enrolled subjects, adverse events (AE) and device deficiencies (DD) will be collected from the time of skin incision until the subject exits. If an AE is considered unresolvable by the investigator, it will be documented within the eCRF that the AE remains unresolved or unrecovered at the time of study exit. Initial reporting of AEs or DDs may be done by phone, email, or by completing as much information as possible on the appropriate eCRF. The completed AE or DD eCRF must be submitted to Medtronic as soon as possible.

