12.2 Device Deficiency

The device deficiency (DD) definition is provided in Table 5: Adverse Event and Device Deficiency Definitions. DD information will be collected throughout the study and reported to Medtronic. Note that a DD that resulted in an AE to the subject should be captured as an AE only.

AFFIX (MaxTack [™] Motorized Fixation Device) Clinical Investigation Plan				
MDT23014	Revision	3.0	Page 50 of 97	Medtronic

In the event of a DD, the device should be returned to Medtronic for analysis, if possible. Instructions for returning the study device will be provided. Device deficiencies should also be documented in the subject's medical record.

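### The device-deficiency endpoint stops on the day of surgery yet names loose and migrated tacks, and the recording rule can remove harmful deficiencies even from that day

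*Protocol*

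**What the plan says.** **Endpoint.** Section 5.2.2 lists as a secondary endpoint the incidence of MaxTack deficiencies, with the examples and window "insufficient tack penetration, loose tacks, tack(s) migration, tacker issue battery etc.) on day of the index procedure". The Synopsis has the same limit: "tacker battery issue, etc.) on the day of the index procedure". Neither place gives a reason for the one-day window.

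**Objective.** Section 5.1.2 sets the secondary objective as safety and performance of the device in "minimally invasive ventral hernia repair procedures within 12 months postoperatively".

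**Collection.** The opening of Section 12 states that for enrolled subjects "adverse events (AE) and device deficiencies (DD) will be collected from the time of skin incision until the subject exits". Section 12.2 repeats it: "DD information will be collected throughout the study and reported to Medtronic". Table 3 schedules a deficiency evaluation on the operative day, at discharge and at Months 1, 3 and 12, and also at any unscheduled visit.

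**Recording rule.** Section 12.2 adds that a deficiency which led to an AE in the subject is entered as an AE and not also as a deficiency.

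**Mechanism.** Among the risks of any tack fixation device, Section 11.1 names "deployed tacks having insufficient holding force (resulting in tack/mesh migration, adhesions, erosion, recurrence and damaged mesh".

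**Imaging.** Section 7.5 requires no equipment to assess endpoints. Imaging is at the physician's discretion, to confirm a recurrence.

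**The concern.** The window suits battery, firing and penetration faults, which the surgeon meets while using the device. It does not suit two of the listed examples. A tack that loosens or migrates after deployment is an implant failure, and Section 11.1 describes tack or mesh migration as a result of deployed tacks not holding. For those two items, an index-day rate captures only what is visible at placement.

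The stake is what the study can report on the device itself. The objective runs to 12 months and results may go to regulators and into publications (Section 4.2). A tack found migrated at Month 1, with no recurrence and no SSO, is recorded but counted nowhere among the endpoints. The AE-only rule adds a second gap: the deficiencies that matter most, those that hurt someone, may be missing from the deficiency count on any day, including Day 0.

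**Working it through.** The protocol states no figure to reproduce, and no sample size, power or alpha rests on this endpoint. The check is a comparison of sections.

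**1. Window against collection.** The visit windows are from Table 4 and the evaluations from Table 3.

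| Deficiency evaluation | Days from surgery | In the endpoint? |
|---|---|---|
| Operative day | 0 | Yes |
| Discharge | 0 or later | Only if discharged on Day 0 |
| Month 1 | 30–51 | No |
| Month 3 | 90–120 | No |
| Month 12 | 365–410 | No |
| Unscheduled | Any | Only if on Day 0 |

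Of the five scheduled evaluations, three never feed the endpoint. It is four for a subject discharged after the day of surgery (3 + 1). This counts assessments, not missed events.

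**2. Where a deficiency found after Day 0 can be counted.** Taking the Section 5.2 endpoints in turn:
- Recurrence (within 1, 3 and 12 months): only if the failure produces a clinical recurrence.
- Reoperation: only if the aim was to repair a recurrent hernia.
- SSO and SSO requiring procedural intervention: only if it shows as a seroma, hematoma, surgical site infection or bleeding at the tack site.
- Pain and HerQLes: scores may shift, but they count no deficiency.
- Fixation time, surgeon satisfaction and length of stay: not relevant.

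A loose or migrated tack seen on imaging, or at an operation done for another reason, therefore reaches no listed endpoint if none of the first three applies.

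**3. Effect of the AE-only rule.** Suppose a deficiency occurs on Day 0.
- If it causes no AE, it is recorded as a deficiency and counted.
- If it causes an AE, it is recorded as an AE only. It is not counted if the endpoint is built from deficiency records.

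Section 5.2.2 does not say which records feed the endpoint, so the second outcome is possible but not certain. Extending the window alone would leave this gap open. The AE items listed in Section 12.4 (such as relationship to device, mesh and procedure, description and outcome) include no separate mark that the event began as a deficiency.

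**4. What later counts can show.** Follow-up is a physical examination with a Valsalva maneuver. No imaging of the tacks and no second look is scheduled. Later loose or migrated tacks will come to light only in subjects who happen to be imaged or reoperated, so any later count is a lower bound.

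**The case against.** **Recurrence is the intended readout.** Section 6.1 says "If the tacks fail in terms of strength or there is a deficiency, it should be observed within 3 months". A reader might infer that the protocol expects deficiencies themselves to be counted over three months. It does not say so. The passage goes on to say that such failure may lead to recurrence, and uses this to justify the 3-month primary endpoint. It names neither migration nor loosening, and a period of three months includes Day 0. This objection stands: the clinical consequence of fixation failure is captured, in the primary endpoint. What remains uncounted is failure without that consequence.

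**Absorption.** Section 7.1 describes tack absorption as minimal in the first two weeks, "with significant absorption from three to five months". It is tempting to read this as proof that the window closes before failures can appear. The documents do not support that. Section 6.1 puts mesh integration at up to 12 weeks, so most of this absorption is designed degradation after the tacks have done their work.

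**Index-day reading.** The examples are illustrative, and a tack that is loose or shifts at placement can be seen on Day 0. The endpoint therefore does not contradict itself, and an index-day rate is a sound measure of delivery and placement. This stands, and is why that rate should be kept.

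**Under-ascertainment.** A 12-month count could be near zero because nobody looked, and could mislead more than the index-day rate. This also stands, and it governs how later counts must be labelled.

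**The analysis plan could add tables.** It could, and all device-related AEs are reported to study exit in any case. But the window is fixed in the protocol's own endpoint definition.

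**Conclusion.** The point holds in a limited form. The endpoint covers Day 0 only and names two kinds of failure that can also arise later. Later deficiencies are collected but reach no listed endpoint unless they appear as a recurrence, a reoperation for recurrence or an SSO. Separately, the AE-only rule can take harmful deficiencies out of the count even on the index day.

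The loss is to the endpoint, not to data collection. Its size in events is unknown, because the protocol gives no deficiency rate. Section 14.8 makes all secondary endpoints descriptive, so the primary inference, power and alpha are untouched.

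A reader might go further and infer that the index-day rate would be presented as evidence of lasting hold. Nothing in the protocol says that, and a rate labelled by its day need not be read that way.

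The conclusion assumes that a deficiency is dated by when it is found, and that the endpoint is built from deficiency records alone.

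**What to change.** In the Synopsis and Section 5.2.2:

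1. Keep the index-day incidence, described as a measure of delivery and placement performance.
2. Add descriptive cumulative counts within 1, 3 and 12 months, using the deficiency evaluations already scheduled. Show implanted-tack deficiencies (loose or migrated) separately from delivery-system deficiencies.
3. State that device-related AEs that arose from a deficiency are counted at every timepoint, including the index day. Keep the recording rule in Section 12.2 if wanted, but make these AEs identifiable, by a mark on the AE form or by review of the event descriptions.
4. Label all postoperative counts as minimum estimates, because tack imaging is not scheduled.

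**Cost.** Endpoint wording, three further timepoints in the tables, and the step that identifies AEs arising from a deficiency. No new visits or assessments are needed. Later counts will be under-ascertained, and the reported deficiency rate may be slightly higher.

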6.1 Rationale

MaxTack[™] Motorized Fixation Device was 510(k) cleared by the Food and Drug Administration (FDA) (US) on September 8th, 2023.

The rationale and justification for the chosen design is based on the evaluation of clinical data from equivalent devices, similar studies ⁽¹⁴⁻²³⁾, and the Instructions for Use (IFU).

Rationale for Prospective, Post-Market, Single Arm-Design

In designing the AFFIX clinical study, Medtronic considered currently available evidence for similar studies ⁽¹⁴⁻²³⁾, feasibility of enrollment, relevant markets/regions, and efficiency of execution, among other factors. A comprehensive literature review was conducted to evaluate the existing body of evidence. Multiple published studies and reports provide substantial data demonstrating the similar devices efficacy and safety in various clinical scenarios ⁽¹⁴⁻²³⁾. These studies collectively establish a substantial foundation of evidence regarding device performance objectives. Additionally, Medtronic has tested the MaxTack[™] Motorized Fixation Device for biocompatibility using standard EN ISO 10993-1 (2009), demonstrating its biological safety.

AFFIX (MaxTac Clinical Invest				
MDT23014	Revision	3.0	Page 25 of 97	Medtronic

The AFFIX study is a US-based, prospective, post-market, multicenter, nonrandomized, single-arm, interventional study that is not mandated by the US FDA. The purpose of this study is to evaluate the performance and safety of the MaxTack[™] Motorized Fixation Device when used for fixation in minimally invasive ventral hernia repair procedures. Due to the substantial evidence on similar devices, a single-arm study design was chosen ⁽¹⁴⁻²³⁾. This study was designed without concurrent treatment control, as a single-arm design was the most feasible and efficient method to achieve the study's objectives for subjects and sites participating in the study. As a single-arm design, the study's primary limitation is, therefore, the lack of a direct comparison to other products on the market.

Rationale for Number of Sites and Subjects

Approximately 10 sites may be selected to participate in the AFFIX study to ensure a multicenter evaluation and to achieve the enrollment goal in a timely manner. The rationale for the sample size of 110 is provided in Section 14.6, Sample Size Determination.

Rationale for Subject Population

The MaxTack[™] Motorized Fixation Device is indicated for use in the fixation of hernia mesh to soft tissue during minimally invasive ventral hernia repair procedures. The subject population will include adult subjects 18 years or older who are undergoing ventral hernia repair by minimally invasive surgeries. Excluding subjects with high risk factors such as infection, American Society of Anesthesiologists (ASA) score of 4, 5, or 6, history of three or more hernia repair surgeries, history of allergic reaction to device components, or a Body Mass Index (BMI) more than 45, may mitigate procedure or device performance risks to the subjects. Restricting enrollment to subjects who have a life expectancy of 3 years or more may aid in ensuring the subjects can complete 12 months of follow-up.

Rationale for Chosen Endpoints and Timing of Endpoints

This post-market study will assess the performance and the safety of the MaxTack[™] Motorized Fixation Device during minimally invasive ventral hernia repair procedures. Subjects will be evaluated at the screening, operative, discharge, Month 1, Month 3, and Month 12 visits.

The primary endpoint of the performance of MaxTack[™] by measuring the incidence of hernia recurrence within 3 months postoperatively has been selected for this study. The absorbable tacks need to retain strength long enough to hold the mesh in place until sufficient ingrowth occurs. Wound healing and mesh integration processes occur up to 12 weeks. If the tacks fail in terms of strength or there is a deficiency, it should be observed within 3 months and may lead to a hernia recurrence during this period. For this reason, having a primary endpoint within the 3 months is appropriate.

The secondary endpoints further evaluate the performance and safety of MaxTack[™]. These include evaluations at Month 1, 3, and 12. Subject follow-up is until 12 months postoperative since the MaxTack[™] tacks will be fully absorbed by 12 months. Based on similar clinical studies, the endpoints were chosen to

AFFIX (MaxTa Clinical Invest				
MDT23014	Revision	3.0	Page 26 of 97	Medtronic

best characterize the performance and safety of MaxTack[™], as well as to evaluate the compatibility and ease of use of MaxTack[™].

Surgical Site Occurrences (SSO) has been defined in this study as the following AEs: Seroma, Hematoma, Surgical Site Infection, and bleeding at tack implantation site. These events were chosen based on previous clinical studies and tailored to the type of events that could occur due to fixation, including tacks ⁽²⁵⁾. Though other events may occur in a subject, these SSOs (beyond hernia recurrence) are the events of interest for this study.

The visit windows for the Month 1, 3, and 12 visits all open on the target date (e.g., Month 1 window begins at 30 days) rather than the allowance for windows to open early. The visit windows are designed to ensure accurate capture of what occurred within that timeframe rather than evaluating the endpoints too early (e.g., within 3 months).

Claims to be verified:

The AFFIX study will verify the following relevant claims related to MaxTack[™]:

- Positive clinical outcomes for fixation of prosthetic material to soft tissue in minimally invasive ventral hernia repair procedures compared to State Of The Art expressed by:
 - the hernia recurrence rate
 - the change in subject Quality of Life (QoL), as measured through the administration o the Hernia Quality of Life Survey (HerQLes) questionnaire (Section 18.4 Appendix D – HerQLes Quality of Life Questionnaire), evaluated at screening and compared to other timepoints
 - the change in subject-reported pain score at the hernia site evaluated with the Numeric Rating Scale (NRS) (Section 18.3 Appendix C – Pain Numerical Rating Scale) at screening compared to other timepoints
- Ability to accommodate physicians in their surgical techniques and clinical cases by enabling prosthetic material fixation to soft tissue: ease of use, compatibility with minimally invasive surgical approach(es) assessed using the Surgeon Satisfaction Questionnaire (Section 18.8 Appendix H – Surgeon Satisfaction Questionnaire).

7. Product Description

